13.1 Study Design and Sample Size Justification

The study design was selected based on the primary aim: to evaluate the ability of CE-MRI and mammography to identify patients for whom IORT is not optimal because of the inability to achieve sufficiently wide surgical margins. If 15% or fewer patients require re-excision, this would be considered acceptable and encouraging for further study; however, a reexcision rate of 30% or higher would not be acceptable.

13.1.1 Accrual to Cohort 1 (Specific Aims 1-3 in Sections 2.1 – 2.3).

Patients will be enrolled in Cohort 1 until 79 patients have received immediate IORT. All patients who are deemed eligible for IORT based on mammography and CE-MRI results will be considered in the decision to stop or continue the trial. There will be one interim analysis when 25 patients have completed WLE and immediate IORT, whether or not additional therapy is needed.

After 25 patients have been evaluated, if 19 or more did NOT require re-excision (based on the surgical specimen), then accrual will continue until 79 patients undergo WLE and immediate IORT. If 7 or more of the initial 25 needed re-excision, then the study will terminate and investigators will conclude that the current method for staging is not sufficiently accurate.

After 79 patients have been evaluated, if 62 or more did NOT need re-excision (based on surgical specimen), investigators will conclude that the chance of correctly identifying a tumor that is suitable for IORT is greater than 70% and that further study of the approach would be justified. If 18 or more of the initial 79 needed re-excision, then investigators will conclude that the chances of correctly identifying a tumor that is suitable for IORT is less than 85%. In this instance, investigators would aim to improve the staging procedures before continuing with this approach.

With this Simon optimal 2-stage design, there will be a 5% chance (alpha) of incorrectly deciding that that approach warrants further study, when the true chance of correctly staging is less than 85%; and there will be a 10% chance (beta) of correctly deciding that this approach warrants further study, when the true chance of correctly staging is greater than 70%.

To evaluate the safety and tolerability of immediate IORT, the following side effects or complications will be taken as evidence that IORT was not well tolerated:

- a. any Grade 2 or greater toxicity

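### Section 13.1.1 states the two-stage error rates under swapped conditions, and its rules count re-excision where 10.1, 13.0 and 13.1.3 count re-excision or mastectomy

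*Combined protocol and SAP*

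**What the plan says.** **Limits.** Section 13.1 treats a re-excision rate of 15% or less as acceptable, and "a reexcision rate of 30% or higher would not be acceptable". As correct staging, these limits are 85% and 70%. The same section explains the design by failures of staging "because of the inability to achieve sufficiently wide surgical margins".

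**Rules in 13.1.1.** Interim: accrual continues if at least 19 of 25 patients did not require re-excision. "If 7 or more of the initial 25 needed re-excision, then the study will terminate". Final: "After 79 patients have been evaluated, if 62 or more did NOT need re-excision (based on surgical specimen"), then "investigators will conclude that the chance of correctly identifying a tumor that is suitable for IORT is greater than 70"%. With 18 or more re-excisions the conclusion is that "the chances of correctly identifying a tumor that is suitable for IORT is less than 85"%.

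**Error rates in 13.1.1.** The design is called a Simon optimal two-stage design with a "5% chance (alpha) of incorrectly deciding that that approach warrants further study, when the true chance of correctly staging is less than 85"% and a "10% chance (beta) of correctly deciding that this approach warrants further study, when the true chance of correctly staging is greater than 70"%.

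**Event elsewhere.** Section 10.1 defines the primary endpoint as re-operation, meaning re-excision or mastectomy. Section 13.0 words the primary aim in the same way. Section 13.1.3 terminates the study once 18 patients need an additional surgical procedure, again mastectomy or re-excision. Section 13.2 summarizes re-operation for inadequate margins or any other reason. Under 7.2.1, DCIS larger than 5 cm can lead to WB-EBRT or mastectomy even with clear margins.

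**The concern.** The error sentence is the only place where the plan states what its go/no-go rule guarantees. Taken at face value, it says that wrong go decisions are held to 5% at any true rate below 85%, and that a worthwhile approach is recognized only 10% of the time. Neither is true of the rule.

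Separately, two sections use the same limit of 18 but name different events. A mastectomy done for a reason other than margins is not a re-excision, so it is not an event under the literal words of 13.1.1. It does count toward the 18 in 13.1.3. The same 79 patients could then be a pass under one section and a termination under the other, on the primary endpoint.

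**Working it through.** **1. Reproduce the plan's design.** Inputs from 13.1 and 13.1.1: unacceptable 70%, acceptable 85%, alpha 5%, beta 10%, n1 = 25, n = 79. In event terms, 25 − 19 = 6, so 7 events stop the study at the interim; 79 − 62 = 17, so 18 events fail at the end.

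Let q be the true chance of correct staging. With 79 − 25 = 54 patients in stage 2 and Y ~ Binomial(54, q):

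P(pass | q) = Σ (x = 19 to 25) C(25, x) q^x (1 − q)^(25 − x) × P(Y ≥ 62 − x)

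At q = 0.70 the seven terms, x = 19 to 25, are 0.0115 + 0.0139 + 0.0122 + 0.0076 + 0.0031 + 0.0008 + 0.0001 = 0.0492. At q = 0.85 the sum is 0.9041, so P(fail) = 1 − 0.9041 = 0.0959.

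A search for the smallest expected sample size at 70%, subject to alpha ≤ 0.05 and beta ≤ 0.10 (total n from 55 to 90), returns exactly these cut-offs: fail at 18 or fewer of 25, or at 61 or fewer of 79. The chance of early stopping at 70% is 0.659, and the expected sample size is 25 + 54 × (1 − 0.6593) = 43.4. The design is therefore what 13.1.1 says it is.

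**2. Compare with the error sentence.**

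| True correct staging | P(pass) |
|---|---|
| 70% | 0.049 |
| 75% | 0.238 |
| 80% | 0.609 |
| 84% | 0.864 |
| 85% | 0.904 |
| 90% | 0.990 |

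- The 5% belongs to 70%. Below 85% but above 70%, the chance of a pass rises to about 90%.
- The 10% is the chance of *failing* at 85% (0.096). The chance of correctly going on there is 0.904.
- P(pass) rises with q, so the correct statements are: at most 5% at 70% or less, and at most 10% failure at 85% or more.

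**3. Counted event.** Take 79 patients of whom 17 need re-excision and one other has a mastectomy for DCIS larger than 5 cm with clear margins (7.2.1). Assume the interim was passed.

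- 13.1.1, read literally: 79 − 17 = 62 without re-excision, which is a pass.
- 13.1.3: 17 + 1 = 18 additional procedures, which terminates the study.

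If both sections count the same event, there is no conflict: 18 events already fail 13.1.1, so stopping at the 18th does not change P(pass).

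**4. How often the rules would disagree.** The share m of Cohort 1 with a mastectomy not driven by margins is not in the documents, so it is an assumption. Each patient falls into one of three classes: re-excision (probability t − m, where t is the total re-operation rate, with margin-driven mastectomy placed here), non-margin mastectomy (m), or neither (1 − t). Disagreement means at most 6 re-excisions in 25 and at most 17 in 79, but 18 or more procedures in total. Exact trinomial sums over stages of 25 and 54:

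| t | m = 0 | m = 1% | m = 2% | m = 3% |
|---|---|---|---|---|
| 15% (the plan's acceptable rate) | 0 | 0.015 | 0.026 | 0.033 |
| 20% (illustrative) | 0 | 0.059 | 0.113 | 0.161 |

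The 20% row is illustrative only: the 20% in 13.0 is a margin-based figure for current practice at the center, not a total re-operation rate in this cohort.

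**The case against.** **On the error sentence**, the best reply is that it is a drafting slip. Aim 1 in 2.1 and Section 13.1 give 15% and 30% correctly, the paragraph just before it attaches a pass to more than 70%, and no trial decision uses the sentence. All of that stands, and it makes the intended design recoverable. It does not make the sentence true.

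**On the event**, re-excision in 13.1.1 may simply be shorthand for the endpoint in 10.1, since 13.1.1 and 13.1.3 share the limit of 18. That is plausible, and a margin-driven mastectomy can fairly be read as a patient who needed re-excision. What remains is the mastectomy for another reason. It is probably uncommon: Cohort 1 requires an imaging size of 4 cm or less, and 7.2.1 also offers WB-EBRT.

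A reader might infer more than the documents support:

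- *That the trial's real error rates are inflated.* They are not; the cut-offs meet 5% and 10%. Treating every direct mastectomy as uncounted would suggest inflation, but that needs a reading in which even margin-driven mastectomies escape the count.
- *That the interim rule conflicts with 13.1.3.* Section 13.1.3 has no limit at 25 patients, so six re-excisions plus one mastectomy breaches nothing there.
- *That 10.1 and 13.0 clearly include size-driven mastectomy.* Both also tie re-operation to margins and link large size to WB-EBRT, so the text supports either answer.
- *That the fail conclusion of less than 85% is unfounded.* It fits the one-sided 10% beta, and the one-sided exact 95% upper limit for 61/79, ignoring the interim, is 84.7%.
- *That a pass claims suitability in a wider sense that includes radiotherapy.* Aim 1 defines suitable candidates by re-excision, so the phrase reads as shorthand.

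**Conclusion.** Two faults of wording stand; the design itself is sound.

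The error sentence is wrong whichever way it is read. Its conditions are interchanged, and beta is attached to the correct decision instead of the missed one. This rests only on the plan's own limits and cut-offs.

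The event mismatch is real but narrow. It matters only if re-excision in 13.1.1 is taken literally and at least one Cohort 1 patient has a mastectomy for a reason other than margins. At the plan's acceptable rate of 15%, and under the assumed 1% to 3%, the two rules would disagree in roughly 1.5% to 3.3% of trials, and never if there are no such mastectomies. It should still be settled, because it defines the event behind the primary decision.

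**What to change.** 1. **Error sentence, 13.1.1.** Restate it as: at most a 5% chance of deciding that the approach warrants further study when true correct staging is 70% or less (event rate 30% or more), and at most a 10% chance of failing to do so when it is 85% or more (event rate 15% or less).
2. **Event, 13.1.1, interim and final.** Replace re-excision by re-operation (re-excision or mastectomy), to match 10.1, 13.0 and 13.1.3. State once whether a mastectomy not driven by margins counts, apply that answer in 10.1, 13.1.1, 13.1.3 and 13.2, and report the other count alongside it. Which answer to choose is for the sponsor.
3. **Margin triggers.** Sections 10.1 and 13.0 use less than 1 mm; 5.3.4 and 7.2.2 use less than 2 mm. These must be reconciled, or the events cannot be counted consistently.

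Cost: a few sentences. Sample size, cut-offs and true error rates stay as they are, and no new data are needed. The one downside is that a pass becomes slightly harder than under the literal 13.1.1 text if non-margin mastectomies count.

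### Section 13.1.1 attaches alpha and beta of the Cohort 1 two-stage rule to the wrong rates (85% and 70% exchanged) and words beta as a correct decision; the sample size and cut-offs fit 70% versus 85%

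*Combined protocol and SAP*

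**What the plan says.** Sections 2.1 and 13.1 fix the two reference rates. On the favourable side, "If 15% or fewer patients require re-excision, this would be considered acceptable and encouraging for further study". On the unfavourable side, "a reexcision rate of 30% or higher would not be acceptable". In terms of correct staging (no re-excision needed), 85% or more is acceptable and 70% or less is not.

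Section 13.1.1 then gives the rule. Stage 1 has 25 patients: continue if at least 19 did not need re-excision, stop if 7 or more did. The final analysis has 79 patients. With 62 or more not needing re-excision, "investigators will conclude that the chance of correctly identifying a tumor that is suitable for IORT is greater than 70"%. With 18 or more needing it, "investigators will conclude that the chances of correctly identifying a tumor that is suitable for IORT is less than 85"%.

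The next paragraph names a Simon optimal two-stage design and states its error rates. Alpha is a 5% chance of "incorrectly deciding that that approach warrants further study, when the true chance of correctly staging is less than 85"%. For beta it gives a "10% chance (beta) of correctly deciding that this approach warrants further study, when the true chance of correctly staging is greater than 70"%.

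**The concern.** The last sentence has two faults.

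- **The rates are exchanged.** Alpha is the chance of going forward when the approach is not good enough, so it belongs to the unacceptable rate, 70%. Beta is the chance of not going forward when the approach is good enough, so it belongs to 85%.
- **Beta is worded as a correct decision.** Read literally, the second half describes a design with 10% power.

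The sentence also contradicts the paragraph directly above it, where success rules out 70% and failure rules out 85%.

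This is the only place where the error rates of the primary decision rule are given; the other alpha and beta values in Section 13.1 belong to the toxicity monitoring rules. A reader who relied on it would take a success as evidence at the 5% level against every rate below 85%, when it is evidence against 70% only.

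**Working it through.** **Inputs (Sections 2.1, 13.1 and 13.1.1).** Unacceptable rate p0 = 1 − 0.30 = 0.70. Acceptable rate p1 = 1 − 0.15 = 0.85. Stage 1: n1 = 25, continue if X1 ≥ 19. Final: n = 79, so 54 further patients, success if the total is ≥ 62. Nominal alpha 0.05 and beta 0.10. The paired cut-offs are exact complements: 25 − 19 + 1 = 7 and 79 − 62 + 1 = 18.

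**Step 1: reproduce the design.** A search over two-stage designs with total n up to 95, for p0 = 0.70, p1 = 0.85, alpha ≤ 0.05 and beta ≤ 0.10, minimising expected sample size under p0, returns n1 = 25, r1 = 18, n = 79, r = 61. Those are the protocol's figures. Expected sample size at 70% is 25 + 54 × (1 − 0.659) = 43.4.

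**Step 2: exact probability of success.** For a true rate p,

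P(success | p) = Σ over x = 19 to 25 of P(Bin(25, p) = x) × P(Bin(54, p) ≥ 62 − x).

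| True rate of correct staging | P(stop at 25) | P(success) |
|---|---|---|
| 70% | 0.659 | 0.049 |
| 71% | 0.618 | 0.071 |
| 75% | 0.439 | 0.238 |
| 80% | 0.220 | 0.609 |
| 84% | 0.092 | 0.864 |
| 85% | 0.070 | 0.904 |

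**Step 3: error rates with the rates in the right place.** Alpha at 70% is 0.049, within 5%. Beta at 85% is 1 − 0.904 = 0.096, within 10%; of this, 0.070 comes from stopping at 25 patients and 0.026 from failing at 79. P(success) rises with p, so these are the worst cases over 70% or less and 85% or more respectively.

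**Step 4: test the sentence as written.**

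- Alpha half: for rates below 85% to carry a 5% bound, P(success) would have to stay at or below 0.05 all the way up to 85%. It is already 0.071 at 71% and approaches 0.904 near 85%.
- Beta half: the chance of deciding for further study at rates above 70% is not 10%. It starts at about 5% and reaches 90% at 85%.
- Check on whether the sentence could describe this rule at all: with the interim rule unchanged, P(success) at 85% falls to 0.05 or below only with a final cut-off of 73 of 79 (0.038; 72 of 79 gives 0.079). The protocol uses 62. This is a consistency check, not a proposal.

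**The case against.** The best case on the other side is that this is an erratum. Everything operational is right: the 15% and 30% reference rates, both interim cut-offs, both final cut-offs and both conclusions. Section 13.1.3 also agrees, ending the study at 18 additional procedures. Those elements, with the named design and the 5% and 10%, determine the intended meaning uniquely. A statistician would see the label beta and recognise a slip, not a design with 10% power, and nobody running the trial would act differently.

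That stands as a limit on the consequences. It does not make the sentence true: the intended meaning has to be reconstructed, and no other place states the error rates correctly.

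A second objection concerns the 80% figure. Section 2.1 quotes a re-excision rate of about 20% as the institution's existing experience, not as a planning value for this study, and 80% lies between the two reference rates, where the protocol calls neither decision wrong. That is fair. The 0.609 shows how far the literal bound is from the rule's behaviour; it is not an error rate of the design.

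Third, confirming the design covers only its arithmetic. Section 7.2.2 advises re-excision for margins under 2 mm, while Sections 10.1 and 13.0 use under 1 mm. Section 13.1.1 counts re-excision, while Section 10.1 counts re-excision or mastectomy. Those passages need reconciling separately and are not settled here.

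**Conclusion.** The concern holds. The error-rate sentence in Section 13.1.1 is false as written in both halves. The rule it describes has alpha 0.049 at a true rate of 70% and beta 0.096 (power 0.904) at 85%, which are the intended 5% and 10% once the rates are put back and beta is worded as an error. The fault is confined to that sentence: sample size, cut-offs, stopping decisions and conclusions do not change. It should be fixed because it misstates the properties of the primary decision rule.

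The calculation assumes independent patients with a common probability of correct staging, all 25 and 79 evaluable, and the cut-offs applied as written.

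**What to change.** Replace the sentence in Section 13.1.1 with text to this effect:

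> Under this Simon optimal two-stage design, if the true probability of correct staging is 70% or lower, the probability of wrongly recommending further study is at most 5% (alpha; exact value 0.049 at 70%). If the true probability is 85% or higher, the probability of wrongly recommending against further study is at most 10% (beta; exact value 0.096 at 85%, power about 90%).

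The exact values are tied to the two reference points, where they are the maxima. The preceding paragraph, the cut-offs and the sample size stay as they are. The cost is one sentence of protocol wording, with no effect on patients, accrual, endpoint or conclusions.

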13.1.2 Accrual to Cohort 2 (Specific Aim 4 in Section 2.4)

While Cohort 1 is open to accrual, as part of this trial, IORT will be offered to patients who have previously (within 3 months) undergone WLE and, based on the surgical specimen, are now considered to be eligible for IORT. Our estimate is that approximately 20 such patients will be enrolled. These patients will be enrolled and treated to document the safety and feasibility of IORT when given in the delayed setting,

For this component of the trial, the following side effects or complications will be taken as evidence that IORT was not well tolerated:

- a. any Grade 2 or greater toxicity
- b. failure for the surgical incision to heal as evidenced by wound dehiscence, wound infection, or skin ulceration.

If 25% or more of Cohort 2 patients experience the above side effects or complications, this will be considered clear evidence that IORT is not well tolerated and will lead to suspension of accrual to this cohort. As above, the decision to continue unchanged, modify the regimen, or terminate the trial will be based on a careful review of all patients treated to date, and all

toxicities and complications experienced. The rules given below will trigger such a review (and are based on the sequential probability ratio test with the theoretical parameters set to $\alpha=0.10$, $\beta=0.10$, $p_o=0.05$, $p_a=0.25$). At the completion of the study, all complications and toxicities will be summarized and reported. During the conduct of the trial, when an unacceptable toxicity or complication (as defined above) is observed, the number of patients (X) who have experienced any unacceptable toxicity or complication will be compared to the number of patients (N) who have begun IORT in this Cohort. If the number of patients, N, is greater than N_x , the number given in the bottom row of the Table 3 then accrual will continue. If N is less than or equal to N_x , then accrual will be suspended for review of the data.

Table 3: Criteria for Suspending Accrual to Evaluate Tolerability

X: # pts with unacceptable toxicity or a complication	2	3	4
N _x : Suspend trial if # patients (N) is $\leq N_x$	≤ 6	≤ 14	≤ 20

These rules were selected to ensure a reasonable chance that the trial would not be suspended if the true chance of unacceptable toxicity were less than 5% and a reasonable chance that it would be suspended if the true chance were 25% to 30% (Table 4). The table below summarizes these probabilities. The values in the table below are based on 10,000 simulations and are accurate to ± 0.01 (based on a 95% confidence interval).

Table 4.

True Chance of Unacceptable Toxicity or Complication	5%	10%	15%	20%	25%	30%
Probability of Suspending Accrual to Review Tolerability	0.05	0.23	0.46	0.67	0.83	0.93

13.1.3 Accrual to Cohort 3 (Specific Aim 5 in Section 2.5)

Cohort 3 will be a subset of patients who begin in Cohort 1 (i.e. are deemed candidates for immediate IORT and who receive immediate IORT) but who subsequently are found to require a mastectomy, re-excision alone, re-excision followed by WB-EBRT, or WB-EBRT alone. This cohort will be followed to monitor and document the complications of the mastectomy and WB-EBRT (with or without re-excision) which are performed following IORT. If all 79 patients are enrolled in Cohort 1 (i.e. the study is not stopped early), then we would expect between 8 and 17 patients requiring an additional surgical procedure (mastectomy or re-excision); as soon as 18 patients require an additional surgical procedure, the study will be terminated.

Using the same definition of unacceptable toxicity as above in 13.1.1 for Cohort 1 and in 13.1.2 for Cohort 2 (any Grade 2 or greater toxicity, or failure for the surgical incision to heal as evidenced by wound dehiscence,

wound infection, or skin ulceration), the rules in Table 3 will also be applied to the patients undergoing an additional surgical procedure in Cohort 3. Separately, we will evaluate the tolerability of WB-EBRT following IORT, in the same manner (using Table 3). Unacceptable toxicity of WB-EBRT include any Grade 2 or greater toxicity, skin flap necrosis, skin ulceration, wound dehiscence, or brachial plexopathy.

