- b. failure for the surgical incision to heal as evidenced by wound dehiscence, wound infection, or skin ulceration.

If 25% or more of Cohort 1 patients experience the above side effects or complications, this will be considered clear evidence that IORT is not well tolerated and will lead to suspension of accrual to this cohort. The decision to continue unchanged, modify the regimen, or terminate the trial will be based on a careful review of all patients treated to date, and all toxicities and complications experienced. The rules given below will trigger such a review (and are based on the sequential probability ratio test with the theoretical parameters set to $\alpha=0.10$, $\beta=0.10$, $p_0=0.05$, $p_a=0.25$). At the completion of the study, all complications and toxicities will be summarized and reported. During the conduct of the trial, when an unacceptable toxicity or complication (as defined above) is observed, the number of patients (X) who

have experienced any unacceptable toxicity or complication will be compared to the number of patients (N) who have begun IORT in this Cohort. If the number of patients, N, is greater than Nx, the number given in the bottom row of the Table 1, then accrual will continue. If N is less than or equal to Nx, then accrual will be suspended for review of the data.

Table 1: Criteria for Suspending Accrual to Evaluate Tolerability											
X: # pts with unacceptable toxicity or a complication	2	3	4	5	6	7	8	9	10	11	12
N _x : Suspend trial if # patients (N) is \leq N _x	≤ 6	≤ 1	≤ 2	≤ 2	≤ 3	≤ 4	≤ 5	≤ 6	≤ 6	≤ 7	≤ 7
	4	1	9	7	5	3	0	8	6	6	9

These rules were selected to ensure a reasonable chance that the trial would not be suspended if the true chance of unacceptable toxicity were less than 5% and a reasonable chance that it would be suspended if the true chance were 25% to 30% (Table 2). The table below summarizes these probabilities. The values in the table below are based on 10,000 simulations and are accurate to ± 0.01 (based on a 95% confidence interval).

Table 2.							
True Chance of Unacceptable Toxicity or Complication		5%	10%	15%	20%	25%	30%
Probability of Suspending Accrual to Review Tolerability		0.07	0.37	0.78	0.96	0.99	0.99

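### Do the tolerability rules in section 13.1 leave it unclear what is suspended after a crossing, and do they have no effect in Cohort 3?

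*Combined protocol and SAP*

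**What the plan says.** Section 13.1.1 sets a sequential tolerability rule for Cohort 1 (Table 1, 79 patients) and 13.1.2 sets one for Cohort 2 (Table 3, about 20 patients). In both, the text says that reaching 25% toxicity "will lead to suspension of accrual to this cohort". The sentence that operates the rule says only that accrual is suspended for data review, with N counted within the cohort. The table titles also refer to accrual, and the result rows of Tables 2 and 4 read "Probability of Suspending Accrual to Review Tolerability". The decision rows of Tables 1 and 3 read "Suspend trial if # patients (N) is", and the rationale sentences below those tables also speak of the trial being suspended.

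Both subsections say that the rules set off a review of everyone treated so far, which may leave the trial unchanged, modify the regimen or end the trial.

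Section 13.1.2 ties Cohort 2 to Cohort 1: "While Cohort 1 is open to accrual, as part of this trial, IORT will be offered to patients" with a recent excision.

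Section 13.1.3 states that "Cohort 3 will be a subset of patients who begin in Cohort 1", followed "to monitor and document the complications of the mastectomy and WB-EBRT" given after IORT. It adds that "the rules in Table 3 will also be applied to the patients undergoing an additional surgical procedure in Cohort 3", and that WB-EBRT after IORT is judged separately from the same table. On numbers, "we would expect between 8 and 17 patients requiring an additional surgical procedure" if Cohort 1 fills. It does not say whose accrual pauses after a Cohort 3 crossing.

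**The concern.** After a crossing in Cohort 2, a reader who follows the text pauses Cohort 2 only; a reader who follows the table row pauses everything. In Cohort 3 the text's action seems to have no object, because the patients have already been enrolled and treated in Cohort 1. Two of the four uses of the rules might then pause nobody, although Specific Aim 5 concerns the safety of exactly this later treatment.

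The printed probabilities would also be at stake. If a crossing in any cohort stops Cohort 1, Table 2 understates the chance that Cohort 1 is paused, since it describes one rule alone. Table 4 is for 20 patients, more than the 8 to 17 expected to have additional surgery. Finally, the rule's N counts patients who have begun IORT, which every Cohort 3 patient did before the additional treatment.

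**Working it through.** **Boundaries.** Inputs from 13.1.1 and 13.1.2: α = β = 0.10, p0 = 0.05, pa = 0.25. The sequential probability ratio test suspends at X events when

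N ≤ X + [X·ln(pa/p0) − ln((1−β)/α)] / ln((1−p0)/(1−pa)),

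with ln 5 = 1.609, ln 9 = 2.197 and ln(0.95/0.75) = 0.2364.

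- X = 2: 2 + (3.219 − 2.197)/0.2364 = 6.3
- X = 3: 3 + (4.828 − 2.197)/0.2364 = 14.1
- X = 4: 4 + (6.438 − 2.197)/0.2364 = 21.9

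Rounded down, these are 6, 14 and 21. Table 3 caps the last at 20. Table 1 is broken in the available text; I read it as 6, 14, 21, 29, 37, 45, 53, 60, 68, 76, 79. The formula gives the same values, with X = 12 (84.4) capped at 79.

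**Printed probabilities.** Let P(n, x) be the chance of x events after n patients without suspension. Then P(n, x) = (1−p)·P(n−1, x) + p·P(n−1, x−1), except that the second term goes to suspension when n ≤ N_x.

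| True rate | Table 2 printed | Exact, N = 79 | Table 4 printed | Exact, N = 20 |
|---|---|---|---|---|
| 5% | 0.07 | 0.064 | 0.05 | 0.054 |
| 10% | 0.37 | 0.374 | 0.23 | 0.231 |
| 15% | 0.78 | 0.781 | 0.46 | 0.467 |
| 20% | 0.96 | 0.962 | 0.67 | 0.681 |
| 25% | 0.99 | 0.997 | 0.83 | 0.834 |
| 30% | 0.99 | 1.000 | 0.93 | 0.924 |

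Agreement is to about 0.01, so both tables are right for one rule run alone.

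**Table 3 at Cohort 3 numbers.** For 8 patients at 5%: two or more events in the first six has chance 1 − 0.95⁶ − 6(0.05)(0.95⁵) = 0.0328. One event in six followed by events in patients 7 and 8 adds 0.2321 × 0.05² = 0.0006. The total is 0.0334.

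| True rate | 8 patients | 12 patients | 17 patients |
|---|---|---|---|
| 5% | 0.033 | 0.042 | 0.051 |
| 25% | 0.488 | 0.662 | 0.773 |

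**Chance that Cohort 1 is paused, all treatments at 5%.** The plan gives no number for WB-EBRT, so I assume 2 to 8 patients: 0.05² = 0.0025 at 2, and 0.0334 at 8. Events under different treatments are taken as independent.

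- Own rule only: 0.0645.
- Adding Cohort 3 surgery: 1 − 0.9355 × 0.9666 = 0.096 (8 patients) to 1 − 0.9355 × 0.9489 = 0.112 (17 patients).
- Adding WB-EBRT as well: 1 − 0.9355 × 0.9666 × 0.9975 = 0.098 to 1 − 0.9355 × 0.9489 × 0.9666 = 0.142.
- Adding Cohort 2 as well (0.0545): 1 − 0.9355 × 0.9455 × 0.9666 × 0.9975 = 0.147 to 1 − 0.9355 × 0.9455 × 0.9489 × 0.9666 = 0.189.

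**The wording, use by use.**

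- *Cohort 1.* Cohort 2 is offered only while Cohort 1 is open. Taken literally, suspending Cohort 1 suspends all enrolment, so text and row ask for the same thing.
- *Cohort 2.* Here alone do text and row differ in effect. The row sits under a title about accrual, and the only sentence that gives a scope says the cohort.
- *Cohort 3, both uses.* The cohort fills only through immediate IORT in Cohort 1, so suspending accrual has a practical meaning. Section 13.1.3 already lets Cohort 3 counts act on the whole study: it terminates at 18 additional procedures. Whatever is paused, the review follows.
- *N in Cohort 3.* Section 13.1.3 names the group as patients undergoing the additional procedure, and separately those given WB-EBRT. Counting those who have started that treatment is the evident adaptation.

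**The case for a change.** The strongest case for a change is that the pause is the rule's immediate protective step, and staff should not have to infer its scope. The loose word is not a single slip either, since it appears in two table rows and in the rationale text. The question could arise in practice: at a 25% complication rate after additional surgery, Table 3 is crossed with probability 0.49 to 0.77. In simulations with 15% re-operated and the plan's own stops in force, the crossing came while Cohort 1 was still enrolling in about 0.61, 0.55 and 0.47 of trials, with events assumed known 0, 10 or 20 enrolments later. Across the readings, the false-pause chance could more than double, from 0.064 to at most 0.189.

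Part of this stands. Section 13.1.3 names no scope, and the 0.83 in Table 4 should not be carried over to 8 to 17 patients. But the spread of the word trial across text and tables points to shorthand, not to two competing instructions. The Cohort 3 rules are not idle under any reading, because the review does not depend on which accrual is paused. Tables 2 and 4 describe each rule in its own cohort and make no study-wide claim. The largest figure requires every rule to stop everything, against the one sentence that states a scope.

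**Conclusion.** No change to the plan follows. The terms are loose and the Cohort 3 scope is unstated, but this is missing detail that those running the trial can fill from the surrounding text. No boundary, printed probability, sample size or conclusion is wrong. The primary re-operation analysis is untouched.

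The effect is limited. With both Cohort 3 rules also pausing Cohort 1, the false-pause chance at 5% toxicity rises from 0.064 to between 0.098 and 0.142, for a temporary halt whose outcome may be to carry on unchanged. This assumes independent events, 8 to 17 re-operated patients as the plan expects, and 2 to 8 WB-EBRT patients, which is my assumption. The scope of a pause remains the sponsor's choice. If the section is edited for other reasons, aligning the terms would be a courtesy to the reader.
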